9.10.3. Other secondary endpoints

All other secondary endpoints will be evaluated in the ITT analysis population using descriptive statistics. No formal hypothesis testing will be performed. The secondary endpoints will be summarized for continuous (n, median, mean, SD, min, max), categorical (counts and percents) or time-to-event data (cumulative incidence), as appropriate.

Other secondary endpoints include:

1. Occurrence of Major Adverse Events (MAEs)
2. Acute procedural success
3. Incidental Target lesion revascularization (TLR)
4. Rate of incidental TLR
5. Improved SBP control assessed at 30-days, 9-months, 12-months, 24-months and 36-months
6. Secondary patency rate at 9-months
7. Change in number and dosage of anti-hypertensive medications
8. Renal function compared to baseline as measured by eGFR at 30-days and 9-months

9.11 Analysis of Safety and Other Parameters

All analyses below will be presented using the ITT analysis population.

9.11.1. Adverse Events

Any untoward medical occurrence observed in a subject or a clinical investigation subject administered an investigational product and that does not necessarily have a causal relationship with this treatment. An AE can therefore be any unfavorable and unintended sign

Confidential

(including any clinically significant abnormal laboratory finding), symptom, or disease temporally associated with the investigational intervention, whether or not considered related to the investigational intervention. Pre-existing conditions, which worsen during a trial, are to be considered AEs. AEs will be coded using Medical Dictionary for Regulatory Activities (MedDRA) version 15.0.

Adverse events will be considered to have occurred after the study procedure in the following situations:

- If the end date of the AE is on or after the procedure date or missing, or the event is ongoing;
- If the day, month, and year of onset are recorded, and the date of onset is the same as or later than the date of procedure
- If the day of onset is missing, and the month and year of onset are the same as or later than the month and year of the procedure;
- If the day and month of onset are missing, and the year of onset is the same as or later than the year of the procedure;
- If the day, month, and year of onset are missing.

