### 6.3 DOCUMENTATION

All AEs must be listed in the subject's source record, transcribed onto on the appropriate eCRF, and will be characterized by the following criteria:

- Intensity or Severity
- Relatedness
- Outcome
- Treatment or Action Taken
- Expectedness

All AEs (serious and non-serious) will be recorded upon completion of the ICF process through the 9-month follow-up visit. Thereafter, only SAEs (for example, those that result in hospitalization, permanent disability, death, or threat of death) will be recorded. All SAEs will be reported to the CEC and DSMB.

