## APPENDIX 4: SCHEDULE OF EVENTS

	(-14)-Days (Medical Documentation Screening period)  Prior to Procedure	(-7)-Days   Prior to Procedure	Day 0  Procedure	30-Days (+14/-7 Days)  Office Visit	6-Months (+/-30 Days)  Phone Call	9-Months (+/-30 Days)  Office Visit	12-Months (+/- 30 Days)  Office Visit	18-Months (+/-30 Days)  Phone Call	24-Months (+/- 60 Days)  Office Visit	36-Months (+/- 60 Days)  Office Visit
Informed Consent	X									
General Entry Criteria	X									
Angiographic Entry Criteria			X							
Demographics and Medical History	X									
Weight (Kg)/ Height (cm)	X									
Vital Signs	X		X	X		X	X		X	X
BP Assessment	X 	X 	X	X		X	X		X	X
Laboratory Assessments	X 		X 	X 		X 				
Test for Proteinuria	X 									
Physical Exam	X		X	X		X	X		X	X
Pregnancy Test	X 		X 							
iCAST™ RX Stent System Placement			X							
Duplex Ultrasound				X		X				
Angiography			X 			X 				
Concomitant Medications	X	X	X	X	X	X	X	X	X	X
Adverse Events	X	X	X	X	X	X	X	X	X	X

A minimum of two office visits are required within the 14-day Medical Documentation Screening period. If the procedure is scheduled > 14 days from the first office visit, subjects should return every two weeks (+/- 3 days) for BP assessments and monitoring.

Chem12 panel which includes: Glucose, Calcium, Albumin, Total protein, Sodium, Potassium, CO2, Chloride, BUN, creatinine, ALP, ALT, AST, and bilirubin.

Test for proteinuria should be completed for subjects during Step 2 of the Medical Documentation Screening Period.

Pregnancy test required at screening and on the day of procedure for females of childbearing potential only.

All subjects must have angiography to determine percent diameter stenosis prior to treatment and at 9-months (if DUS indicates ≥ 60% stenosis).

AE collection (serious and non-serious) will begin upon completion of the ICF process through the 9-month follow-up visit, thereafter only SAEs and UADEs will be recorded.

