7.3 Handling of Missing Date/Time Data

7.3.1. Missing Date

It is preferred that the day and month of all medical history and other baseline characteristics dates will be known. If the date's day of the month is missing such that a determination of whether the event occurred within the reporting window cannot be made, the day will be imputed as follows:

- If only the month of the event is known, then the 1th day of this month will be imputed for a missing day.
- If only the year of the event is known, then the 1st of January will be imputed for a missing, day and month.
- For events occurring between two visits after enrollment, without other information available, the date in the middle of these visits will be used.

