Change from baseline in the antihypertensive medication dosage = (Dosage of anti-hypertensive medication at follow-up – the dosage of the anti-hypertensive medication at baseline).

An indicator variable which identifies any increases in dosage (change from baseline > 0) will also be derived.

9. Renal function compared to baseline as measured by eGFR at 30-days and 9-months.

Renal function will be assessed by eGFR at the 30-days and 9-months of study follow-up. eGFR results will be estimated by the abbreviated Modification of Diet in Renal Disease(MDRD) equation : $186 \times (\text{Creat} / 88.4) - 1.154 \times (\text{Age}) - 0.203 \times (0.742 \text{ if female}) \times (1.210 \text{ if black})$.

The change from baseline in eGFR will be computed as follows:

Change from baseline in eGFR = (eGFR result at follow-up – eGFR result at baseline)

- i. In addition, an indicator variable will be derived in order to identify decreases from baseline in eGFR of >25%, >40%, >50% at any time point.

Amendment #1: 15Jul13

7.6.3.Safety Outcomes and Other Parameters

The main safety outcome is the incidence of subjects with any adverse event experienced after the study procedure has occurred over the totality of the study.

Other parameters collected to monitor safety and/or to derive efficacy include:

- Vital signs (systolic and diastolic blood pressure)
- Laboratory Assessments (chemistry, urine analysis, proteinuria, eGFR)
- Physical Examination (assessment of general appearance, abdomen, cardiovascular, dermatologic, genitourinary, head, eyes, ear, nose and throat (HEENT), lymph nodes, musculoskeletal, neurological, respiratory)
- Duplex Ultrasound (degree of stenosis)
- Angiography (degree of stenosis)
- Revascularization (number of revascularization, location, type)
- Concomitant medications/antihypertensive medications
- Mortality

8. STATISTICAL METHODS**8.1 General Statistical Considerations**

Data collected in this study will be presented using summary tables and subject data listings.

Demographic, endpoint information, safety data and other parameters will be summarized and presented for the ITT and Per-Protocol populations accordingly. Summaries for continuous and ordinal variables will include the number of observations (n), arithmetic mean, standard deviation (SD), minimum (min), maximum (max), median, and 95% confidence intervals of the means.

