Adverse event data summaries will be presented by System Organ Class (SOC) and Preferred Term (PT). AEs will be summarized using discrete summary statistics at the subject and event level by SOC and PT. If a subject reports the same PT multiple times within the same SOC, that PT will only be reported once within that SOC. As with the PT, if a subject reports multiple conditions within the same SOC, that SOC will only be reported once.

To count the number of subjects with any AEs, if a subject has multiple AEs coded to the same PT within the same SOC, the subject will be summarized within the maximal severity. For the summary of maximal severity, if the subject has multiple AEs of the same PT and of different grades of severity, the maximal severity will be reported. In the summary, SOC will be listed in ascending alphabetical order; PTs will be listed in order of descending frequency for all subjects within each SOC.

Separate summaries of the AEs stratified by before or after study procedure will be provided for the following categories:

- Adverse Events (AE)
- Procedure-Related AEs
- Unanticipated Adverse Device Effects (UADEs)
- Serious AEs (SAE)
- Serious Procedure Related AEs (separate for CEC adjudicated events and Investigator)
- Fatal AEs

All AEs will be presented in a subject listing. In addition, UADEs will be provided in a
Amendment #1: 15Jul13

separate listing.

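### SAP 9.11.1 does not join its end-date condition to its onset conditions, so adverse events that began, or even ended, before the procedure can be counted as post-procedure

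*SAP*

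**What the plan says.** SAP 9.11.1 introduces the rule with "Adverse events will be considered to have occurred after the study procedure in the following situations" and gives five bullets.

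- The first concerns the end of the event: "If the end date of the AE is on or after the procedure date or missing, or the event is ongoing".
- The second concerns a complete onset date, which must not precede the day of stenting: "If the day, month, and year of onset are recorded, and the date of onset is the same as or later than the date of".
- The last three concern onset dates with the day missing, with day and month missing, and wholly missing. Each places the event after the procedure unless the known part of the onset date is earlier.

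No word links the first bullet to the others, and nothing elsewhere in the SAP limits it.

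The classification is used in two places. The main safety outcome (SAP 7.6.3, repeated in 9.11.4) is the incidence of subjects with "any adverse event experienced after the study procedure has occurred". SAP 9.11.4 adds: "Separate summaries of the AEs stratified by before or after study procedure will be provided". The categories there are all AEs, procedure-related AEs, unanticipated adverse device effects (UADEs), serious AEs (SAEs), serious procedure-related AEs and fatal AEs.

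Pre-procedure events will be in the database. Protocol 6.3 says "All AEs (serious and non-serious) will be recorded upon completion of the ICF process through the 9-month follow-up visit", and the schedule in Appendix 4 agrees: "AE collection (serious and non-serious) will begin upon completion of the ICF process through the 9-month follow-up visit".

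A separate section on missing dates, SAP 7.3.1, says: "If only the month of the event is known, then the 1th day of this month will be imputed for a missing day".

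**The concern.** A before/after split of AEs should rest on when the event began. The first bullet has no onset condition. Suppose renal function worsens from Day -10, with that date fully recorded, and has not resolved by Day 0. Under the first bullet it is a post-stent AE, although the onset test in the second bullet would put it before the procedure. The last three bullets have the opposite gap: they have no end-date condition, so an event with an incomplete onset date can be placed after the procedure although its recorded end date is earlier.

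The trial has one arm, so there is no control group in which the same miscount would appear. The SAP also makes all inferential analysis descriptive after the early stop of enrolment, so these counts and percentages are themselves the safety result. Events present before the stent would be shown as arising after it, and the pre-procedure background would look smaller than it was.

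**Working it through.** **Inputs**

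- Classification rule: SAP 9.11.1.
- Start of AE recording: consent (Protocol 6.3, Appendix 4), with AE collection also at the Day -7 and Day 0 visits (Protocol 4.1.2 and 4.2.1).
- Screening: at least 14 days, with two-weekly visits if the procedure is later. Subjects with a documented stable regimen may skip the formal period (Protocol 3.4).
- Denominator: 68 enrolled subjects (SAP 6.1), intent-to-treat population (SAP 9.3, 9.11).
- The documents state no AE rate for this rule, so there is no plan figure to reproduce.

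**Step 1: the two readings.** Let E be the first bullet (end date on or after the procedure, end date missing, or event ongoing). Let O mean that one of the four onset bullets holds. As written, with each situation sufficient, an event is after the procedure if E **or** O. If the first bullet is a precondition, it is after only if E **and** O.

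| Event | E | O | E or O | E and O |
|---|---|---|---|---|
| Complete onset on or after Day 0 | yes | yes | after | after |
| Complete onset before Day 0; ongoing, no end date, or ends on/after Day 0 | yes | no | **after** | before |
| Complete onset before Day 0; ended before | no | no | before | before |
| Onset in procedure month, day missing; ended before | no | yes | **after** | before |
| Onset wholly missing; ended before | no | yes | **after** | before |
| Onset partial or missing, could be after; not ended before | yes | yes | after | after |

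The readings differ only in the bold cells. In each of those the event certainly began before the procedure.

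**Step 2: enumeration.** Every onset from day -60 to +60 was crossed with every end date from onset to day +120, or no end date, with the procedure on 15 March.

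- Onset before and end on/after the procedure or missing: 60 × (121 + 1) = 7,320 combinations. With complete onset dates, 7,320 of 7,320 are classed as after under E or O, and 0 under E and O.
- Onset and end both before the procedure: 1 + 2 + … + 60 = 1,830 combinations. Under E or O, the number classed as after is 0 with complete onset, 105 with the day missing (the 14 earlier days of the procedure month: 14 × 15 / 2), and 1,830 with day and month missing or the whole date missing. Under E and O it is 0 throughout.
- Onset on or after the procedure: 5,612 combinations, all classed as after under both readings.

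These counts show which cases the rule catches. They are not expected frequencies. No true post-procedure event is ever lost, so the error runs one way.

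**Step 3: size for the subject-level outcome.** If m subjects have a carry-over event as their only post-procedure AE, the incidence rises by m/68: 1/68 = 1.5 points, 3/68 = 4.4, 5/68 = 7.4, 10/68 = 14.7.

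Let q be the proportion of subjects with a carry-over AE and b the proportion with a true post-procedure AE. Both are assumed, and independent. Inflation in points = 100 × (1 − b) × q.

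| b | q = 5% | q = 10% | q = 20% |
|---|---|---|---|
| 60% | 2.0 | 4.0 | 8.0 |
| 80% | 1.0 | 2.0 | 4.0 |
| 90% | 0.5 | 1.0 | 2.0 |

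The range of 0.5 to 8.0 points is 0.005 × 68 = 0.3 to 0.08 × 68 = 5.4 subjects. Event-level counts in the all-AE tables rise for every carry-over event, whatever b is.

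**The case against.** The strongest reply is that the first bullet was meant as a precondition. This has force. Under the as-written reading the second bullet is redundant, because an event that starts on or after the procedure cannot end before it, so the first bullet already catches it. Bullets three to five would then add only events that had already ended before the procedure, which nobody would want. The four onset bullets exclude one another, but that does not settle how the first bullet combines with them. What stands is that the SAP does not state the precondition, and the two readings give different tables.

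A second reply is that over-counting post-device AEs cannot hide harm, that the outcome has no test or performance goal, and that all AEs are listed by subject. This is true and limits the consequence. The published percentages would still be wrong and the pre-procedure background understated.

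A third is that an event still ongoing is experienced after the procedure. That would make an onset test pointless. Where the SAP does want carry-over counted, as for concomitant medications in 9.8, it says so. A pre-existing condition that worsens is an AE under 9.11.1, but the first bullet does not ask for worsening.

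Three stronger readings may tempt a reader, and the documents do not support them:

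- **Inflation of 4 to 21 points.** With 5–20% of 68 subjects carrying over (about 3 to 14 subjects), 3/68 = 4.4 and 14/68 = 20.6. This requires that none of them has a true post-procedure AE, although all AEs are recorded to 9 months and SAEs after that. It is an upper bound on an assumed rate.
- **All the split tables are distorted alike.** An event that began in screening should not be judged procedure-related or a device effect, so those tables should move little. The major adverse event endpoint uses committee-adjudicated data (SAP 4).
- **SAP 7.3.1 contradicts 9.11.1.** Section 7.3.1 opens with medical history and baseline dates. One of its bullets mentions events after enrolment, so its reach is unclear, but 9.11.1 has its own partial-date rules and the specific rule reasonably governs.

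**Conclusion.** The point holds as a defect in the wording of one derivation rule. Taken literally, SAP 9.11.1 counts fully dated screening-onset events as post-procedure when they are unresolved at Day 0, and can do the same to incompletely dated events that had already ended. Compared with a rule based on onset, this can only raise the main safety outcome and the all-AE and SAE counts after the procedure, and lower the counts before it.

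The size cannot be fixed from the documents. The sure statement is 1.5 points per subject whose only post-procedure AE is a carry-over. The 0.5 to 8 points rests on the assumed proportions and on independence. Shorter exposure in subjects who skip formal screening would tend to reduce it. If the programmer already applies the first bullet as a precondition, the tables are right and only the text needs correcting.

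**What to change.** Reword SAP 9.11.1 so that an AE is post-procedure only if the first condition holds **and** one of the four onset conditions holds. A complete onset date then decides the class. A partial or missing onset date counts as post-procedure only if the known part of the date allows it and the event did not end before the procedure. Some incompletely dated events that truly began earlier will still default to after, which is a reasonable convention once stated.

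List events with onset before the procedure that are ongoing at Day 0 separately, so that they remain visible. State that the partial-date rules in 9.11.1, and not 7.3.1, govern AE timing.

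Three additions should be avoided. Imputing a partial onset to the later of the first of the month and the procedure date fails when the known month is earlier: an onset in May with a procedure on 15 June would become 15 June. Requiring an onset time, or re-entering worsened events as new AEs with a worsening date, may need data that were not collected; neither item is among the minimum AE source fields in Protocol 8.4.

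The cost is a few lines of SAP text, one derivation rule and one extra listing. The rule uses the onset date, end date, ongoing status and procedure date that 9.11.1 already relies on.

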9.11.2. Serious Adverse Events (SAE)

Any adverse experience that results in any of the following outcomes:

- Death
- Is life-threatening
- Subject hospitalization or prolongation of existing hospitalization
- A persistent or significant disability or incapacity
- Congenital anomaly or birth defect
- Important medical events that may not be immediately life-threatening or result in death or hospitalization, but may jeopardize the subject or may require intervention to prevent one of the outcomes listed in the definition above.

9.11.3. Unanticipated Adverse Device Effect (UADE)

Any serious adverse effect on health or safety, or any life-threatening problem or death caused by, or associated with, a device, if that effect, problem, or death was not previously identified in nature, severity, or degree of incidence in the Investigational Plan or Instructions For Use (IFU), or any other unanticipated serious problem associated with a device that relates to the rights, safety, or welfare of subjects.

9.11.4. Anticipated Adverse Events

Based on the literature and on clinical and commercial experience with implantation of a covered stent in human arteries,

Table 4: Anticipated AEs, includes anticipated AEs that have been identified as possible complications:

Table 4: Anticipated AEs

 ○ Abdominal Pain ○ Abscess ○ Acute or sub-acute thrombosis ○ Acute myocardial infarction ○ Allergic reaction to stainless steel, drugs, contrast agent, or anti-platelet agents ○ Aneurysm ○ Arrhythmias, including Ventricular Fibrillation (VF) and Ventricular Tachycardia (VT) ○ Arteriovenous (AV) fistula ○ Bowel infarct ○ Death ○ Dialysis ○ Emboli (air, tissue, or thrombotic) resulting in tissue ischemia or infarction ○ Emergency surgery to correct vascular complications ○ Extremity ischemia/amputation ○ Fever ○ Hemorrhage ○ Hematoma 	
 ○ Hypotension or hypertension ○ Inadequate implantation or Intimal trauma ○ Inadvertent exclusion of branch or accessory vessel ○ Incision site pain or infection ○ Injury, dissection, perforation, or rupture of the vessel ○ Kidney infarct ○ Myocardial infarction or ischemia ○ Nephrectomy ○ Pseudo-aneurysm formation ○ Pyrogenic reaction ○ Renal insufficiency or failure ○ Restenosis of stented lesion ○ Sepsis/infection ○ Stent embolization ○ Stent migration/stent misplacement ○ Stroke or other cerebrovascular accident ○ Thromboembolic event ○ Tissue necrosis or ulceration ○ Total occlusion ○ Vessel spasm
---	--

The study main safety outcome is the incidence of subjects with any adverse event

Amendment #1: 15Jul13

Confidential

observed after the study procedure over the totality of the study. An overall summary that includes the incidence of subjects with any adverse event during the entire study, the number of AEs and the number and percentage of subjects who experienced at least one AE will be presented. This summary will also include all AEs, serious AEs (SAEs), unanticipated adverse device effects (UADE), procedure-related AEs, procedure related SAEs and AEs with outcome of death.

Adverse event data summaries will be presented by System Organ Class (SOC) and Preferred Term (PT). AEs will be summarized using discrete summary statistics at the subject and event level by SOC and PT. If a subject reports the same PT multiple times within the same SOC, that PT will only be reported once within that SOC. As with the PT, if a subject reports multiple conditions within the same SOC, that SOC will only be reported once.

To count the number of subjects with any AEs, if a subject has multiple AEs coded to the same PT within the same SOC, the subject will be summarized within the maximal severity. For the summary of maximal severity, if the subject has multiple AEs of the same PT and of different grades of severity, the maximal severity will be reported. In the summary, SOC will be listed in ascending alphabetical order; PTs will be listed in order of descending frequency for all subjects within each SOC.

Separate summaries of the AEs stratified by before or after study procedure will be provided for the following categories:

- Adverse Events (AE)
- Procedure-Related AEs
- Unanticipated Adverse Device Effects (UADEs)
- Serious AEs (SAE)
- Serious Procedure Related AEs (separate for CEC adjudicated events and Investigator)
- Fatal AEs

All AEs will be presented in a subject listing. In addition, UADEs will be provided in a
Amendment #1: 15Jul13

separate listing.

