#### 6.3.2 RELATEDNESS

The Principal Investigator (PI) will evaluate if the AE or SAE is related to the investigational device. Relatedness is defined in the following manner:

- Not related: The PI has determined that the complication is not related to the trial device.
- Unlikely: The current state of knowledge indicates that a relationship to the use of investigational device is unlikely.
- Possibly or Probably: The PI has determined that the event has a reasonable relationship to the use of the investigational device.
- Definite: The PI has determined that the complication is related to the investigational device.

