## **8.4 SOURCE DOCUMENTATION REQUIREMENTS**

Regulations require that Investigators maintain information in the trial subject's medical records which corroborate data collected on the eCRF. In order to comply with these regulatory requirements, the investigator will maintain and make available as required by monitors, Atrium or its designated CRO, and/or its regulatory inspectors the following information that includes but is not limited to:

- Signed ICFs and associated documents.
- Medical history/physical condition of the trial subject before involvement in the trial sufficient to verify protocol entry criteria.
- Dated and signed notes in the subject's medical record on the day of entry into the trial that identify: the subject's date of entry into the trial, the clinical site, subject's assigned number, and a statement that ICF was obtained.
- Dated and signed notes for each trial subject visit with reference to the eCRFs for further information, if appropriate (for specific results of procedures and exams).

- Description of device implantation procedure (material used, drugs administered during the procedure, date, time duration, angiographic, US and clinical findings, etc.).
- Notations on abnormal lab results and their resolution.
- Dated printouts or reports of special assessments, i.e. angiography, echo doppler, CT, X-rays, laboratory tests.
- AE reporting and follow-up of the AEs (minimally event description, severity, onset date, duration, relation to trial device, outcome and treatment for AEs).
- Notes regarding concomitant medications taken during the trial (including start and stop dates).
- Trial subject's condition upon completion of or withdrawal from the trial.

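### SAP 9.11.4 summarises related adverse events only by relation to the procedure, while the protocol has investigators rate relation to the device, so the SAP text calls for no device-related AE or SAE rate

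*SAP*

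**What the plan says.** Protocol 6.3.2 sets one causality question for the investigator: "The Principal Investigator (PI) will evaluate if the AE or SAE is related to the investigational device". The four answers are Not related, Unlikely, Possibly or Probably, and Definite, and all concern the device. Protocol 8.4 lists what the source record must hold for each AE, including "relation to trial device, outcome and treatment for AEs". Neither section asks the investigator to rate relation to the procedure.

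SAP 9.11.4 describes an overall AE summary covering all AEs, SAEs and UADEs, and then "procedure-related AEs, procedure related SAEs and AEs with outcome of death". It goes on to list separate SOC/PT summaries. Two of those are related-event categories: procedure-related AEs and "Serious Procedure Related AEs (separate for CEC adjudicated events and Investigator". No device-related AE or SAE category is listed, and the SAP does not say which ratings count as related.

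**The concern.** The causality rating that the protocol requires is not the one that the SAP summarises. The one that the SAP does summarise, including an investigator version, has no rating scale in the protocol.

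The primary objective (SAP 4) includes the safety of the stent system. The implant stays in place, and Protocol 6.3 keeps SAE collection going after the 9-month visit. An investigator could judge a late event in the stented segment to be related to the device but not to the index procedure. Under the SAP as written, that judgement would enter no related-event table.

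Descriptive tables also carry more weight here than was first planned. Enrollment stopped at 68 subjects (SAP 6.1), and SAP 2 says that all inferential analysis is to be read as descriptive.

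**Working it through.** No arithmetic decides this point. The check compares what is rated with what is tabulated.

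**Rated by the investigator:** relation to the device, for every AE and SAE (Protocol 6.3.2), and recorded in source (Protocol 8.4).

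**Outputs in the SAP text that carry any attribution:**

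| Output | SAP section | Attribution | Device-related AE or SAE rate? |
|---|---|---|---|
| Overall AE summary | 9.11.4 | Two related rows, both procedure | No |
| SOC/PT summaries | 9.11.4 | Two related categories, both procedure; the serious one in CEC and investigator versions | No |
| UADE summary and listing | 9.11.3, 9.11.4 | Device, but in effect only unanticipated serious effects | No |
| MAE, death component | 7.6.2 | Procedure or device, pooled; deaths only | No |
| Device failures, malfunctions, misuse | 9.11.5 | Incident counts; the listing flags an AE tied to a performance issue | No |
| Death listing | 9.11.13 | Device; deaths only | No, a listing |
| Listing of all AEs | 9.11.4 | Columns not specified | No, a listing |

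**Whether UADEs fill the gap.** A UADE is a serious effect or problem that, in the main limb of the definition, "was not previously identified in nature, severity, or degree of incidence in the Investigational Plan or Instructions For Use (IFU". SAP Table 4 already names 17 + 20 = 37 anticipated event types, among them thrombosis, restenosis, total occlusion and stent migration. A device-related event of one of these types would normally not be a UADE unless its severity or frequency went beyond what was identified. Non-serious device-related events fall outside the category. So the UADE table cannot stand in for a table of device-related events.

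**What is reported whatever the attribution.**
- Total occlusion and clinically driven re-intervention enter primary patency (SAP 7.6.1, 9.9.1).
- Clinically driven and incidental TLR are both derived (SAP 7.6.2).
- Duplex stenosis below 60%, or 60% and above, is counted at follow-up (SAP 9.11.8).
- Target vessel revascularization is summarised (SAP 9.11.11).
- Anything reported as an AE or SAE enters the all-AE and SAE tables (SAP 9.11.4).

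The gap is therefore in the attribution summary and not in the capture of events.

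**The case against.** The strongest reply is that the important device harms are reported anyway through patency, TLR, duplex, revascularization and the all-AE tables. That stands, and it limits the consequence. It does not supply a summary of the investigator's device rating, which is a different quantity.

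Second, SAP 11 leaves the complete list of outputs to separate table mock-ups, and the eCRF is not among the public documents. A device-related table may exist in the first and a procedure-relatedness field in the second. The CEC and investigator split in SAP 9.11.4 suggests such a field. This also stands, so the claim here is limited to what the SAP text calls for.

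Third, procedure-relatedness is not foreign to the protocol. The MAE endpoint (Protocol 2.3, Appendix 2) is defined as procedure-related and includes procedure- or device-related death. What the protocol lacks is a scale on which the investigator rates it.

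A reader might go further and infer that device-relatedness is never reported, or appears only in the death listing. The table of outputs above shows otherwise.

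A reader might also apply Protocol Table 6 to the 68 enrolled subjects and infer that up to 0.21 × 68 = 14.3 with restenosis and 0.02 × 68 = 1.4 with total occlusion would be missing from the related-event tables. The documents do not support that:
- Both percentages are upper bounds.
- Table 6 is headed as events related to stent placement.
- The MAE definition already places clinically driven TLR among procedure-related events, and MAE are reported to 36 months.

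Nothing shows how many such events would be rated device-related but not procedure-related.

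**Conclusion.** The mismatch is real. The protocol requires a device-relatedness rating for each AE and SAE, and the SAP text calls for no rate of device-related AEs or SAEs. Both related rows of the overall summary, and both related categories of the SOC/PT summaries, use relation to the procedure.

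The effect is a missing safety summary. It is not a loss of events, and the primary endpoints are unaffected. No number of affected subjects can be given. The documents also do not show that total device harm would be understated, because the events appear elsewhere.

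The conclusion assumes that the SAP text governs the outputs and that the 6.3.2 rating was collected as the protocol requires. If the mock-ups already include device-related tables, what remains is to state them, and the rule for counting an event as related, in the SAP.

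**What to change.** In SAP 9.11.4:

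1. Add device-related AEs and device-related SAEs to the overall summary and to the SOC/PT tables, by subject and by event, beside the procedure-related ones.
2. Take the rating from Protocol 6.3.2. Count Possibly or Probably and Definite as related, and Not related and Unlikely as not related.
3. State the data source for each version of procedure-relatedness: the eCRF field behind the investigator version, and the scope of adjudication behind the CEC version. Naming the CEC as the sole source would conflict with the investigator version that SAP 9.11.4 already lists.
4. Note under the tables that all AEs are collected to the 9-month visit and only serious events after it (Protocol 6.3; Appendix 4 adds UADEs), so device-related non-serious events are covered only to 9 months.

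The cost is SAP wording and a few extra tables from data already required. No protocol amendment is needed.
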